1.1 Primary Objective

1a. To evaluate pain-related fear outcomes between GET Living and TPM. Hypotheses: Compared to TPM, the GET Living group will (1) have significantly less pain-related fear avoidance (adolescent, parent) at discharge, with continued gains at 3 and 6-month follow-up; Exploratory: (2) have fewer number of days to pain-related fear avoidance improvement via daily diaries.

1b. To evaluate disability and parent responses to pain outcomes between GET Living and TPM. Hypotheses: Compared to TPM, adolescents receiving GET Living will have (1) significantly less functional disability and protective parent responses at discharge, with continued gains at 3 and 6-month follow-up; Exploratory: (2) fewer number of days to achieve decreased functional disability and protective parent responses, assessed via daily diaries; (3) significantly better adolescent joint kinetics at discharge, assessed via motion analysis; and (4) demonstrate significantly greater increases in daily physical activity levels at discharge via Actigraphy. We will also examine treatment response correlates: age, pain, gender, diagnosis, and readiness to change.

2. To characterize feasibility and acceptability of GET Living compared to TPM to inform implementation of a large multi-site RCT. Hypotheses: GET Living participants will have (1) high treatment satisfaction ratings (mean score \geq 40 of 60; reflective of satisfied or very satisfied); Secondary: (2) \geq 80% sessions completed on-schedule, \leq 20% attrition rate, \geq 80% adolescent and parent daily diary adherence; Exploratory: (3) fewer health care costs at 3 and 6-month follow-up compared to TPM.

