
biostatistician will also create a randomization scheme to determine the number of days for the pre-treatment baseline period for each individual participant (2 weeks on average).

Study Procedures. At the BAS visit participants will complete informed assent/consent, complete baseline questionnaires, begin daily diaries, and begin wearing an Actigraph. Child participants will undergo biomechanical assessment (**[name]**, Director of the Motion and Sports Performance Laboratory at SCH) during this visit. Notification of treatment arm allocation will occur at the end of the pre-treatment baseline period, and treatment will begin according to randomized group allocation: GET Living or TPM. Discharge testing occurs at the end of GET Living or TPM and includes participant questionnaires, child biomechanical assessment, and an exit interview. Daily diary and actigraphy ends at discharge. At 3 and 6 months follow-up, participants complete daily diaries for 7-days and self-report questionnaires.

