Treatment Conditions. Participants will be randomized into: **GET Living or Typical Pain Management (TPM)**. During the study, participants will be instructed to not seek new treatments for pain. **GET Living.** An outpatient team consisting of a pain psychologist and physical therapist (PT) provide GET Living, both trained in this modality of treatment by [name] with ongoing consultation from [name] (lead innovator of GET in adults) and exposed to treatment session videos from participants in the pilot. GET Living is focused and individually tailored. The primary aim of GET Living is returning to valued activities of daily life and restoring daily functioning, including return to school. The treatment manual, entitled **GET Living: Graded Exposure Treatment for children and adolescents with chronic pain** was adapted from the adult treatment manual⁴⁹ (see **Section 5.1** detailed description). The protocol consists of 12 50-minute sessions delivered twice a week for up to 12 weeks. Sessions 1-5 (education, formulation, goals) are conducted with the psychologist, PT, adolescent, and parent. Graded exposure begins in session 6. The psychologist and PT co-lead a portion of the exposure sessions. During the remaining exposure sessions, the PT leads the exposures while the pain psychologist meets individually with the parent. The final two sessions focus on relapse prevention and future goal setting. **Typical Pain Management.** After randomization, participants allocated to the TPM group will initiate treatment, as indicated by the TPM treatment manual. To ensure dose equivalency, we increased this to 6-Psychology/6-PT with 3 parent-only sessions. In pain management psychology⁵⁰ child and parent sessions focus on biopsychosocial model education, goal setting, pain coping skills training, and cognitive restructuring. PT sessions are based on Guide to Physical Therapy Practice 3.0⁵¹ consisting of 1) therapeutic exercise, 2) balance and proprioception, 3) strength training, and 4) use of modalities (e.g., heat/cold pack).

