5. STUDY INTERVENTIONS

5.1 Interventions, Administration, and Duration

GET Living: Participants randomized into the **GET Living** intervention group, will participate in 12 sessions, 1-hour each, delivered twice a week over for up to 6 weeks.

Phase I-III. The goals of Phase I-III are to educate the participants about the fear avoidance model of pain (individual and interpersonal), present the treatment rationale and formulation, create values-based treatment goals to enhance motivation, and create a pain-related fear hierarchy from the PHODA-YE results to design specific exposures. The pain psychology therapist (PSY) and PT are both present for these sessions to ensure that the treatment message is consistent from both providers to the family. Most of these activities are conducted jointly with the adolescent and parent present, although this varies with the developmental level of the adolescent. For example, while younger adolescents require parental input when developing fear hierarchies, most older adolescents do not want or need parent involvement to complete this task. In addition, depending on parent awareness of their own distress and behavior that may be impacting their adolescent's functioning, the interpersonal fear avoidance model formulation may initially be presented separately. The decision on whom to include for the different treatment exercises in these initial sessions will be jointly negotiated by the therapists, patient, and parents.

Phase IV. Graded Exposure consists of engaging in activities perceived as potentially 'harmful' or 'worrisome' in a controlled and continuous manner in order to elicit anxiety and to foster habituation and the subsequent

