Typical Pain Management (TPM) is a treatment intervention that is representative of current standards of care in a multidisciplinary pain clinic setting. We calculated historical PPMC treatment data for patients who met enrollment criteria (Mean sessions: Psychology=5 and PT=4). To ensure dose equivalency, we increased this to 6-Psychology/6-PT with 3 parent-only sessions. The CBT has been adapted from published manual for CBT treatment

of pediatric chronic pain and depressive symptoms ⁵² and the PT sessions are based on Guide to Physical Therapy Practice 3.0⁵¹.

Overview. The protocol consists of approximately 12 sessions, 1-hour each, delivered twice a week, on average for 6 weeks. Patient and parent will complete daily diaries and patients will wear the Actigraph throughout the duration of treatment. Sessions will alternate between psychological CBT sessions and Physical Therapy sessions, as outlined in Table 2 below. 3 Parent-only CBT sessions with the pain psychologist will be included to address parental coping skills.

Cognitive Behavioral Therapy (CBT). CBT will consist of 6 patient sessions and 3 parent-only sessions with a licensed pain psychologist focused on biopsychosocial model education, goal setting, coping skills training, and cognitive restructuring. The final CBT sessions with the psychologist will focus on relapse prevention, long term goals, reviewing of accomplishments during treatment.

Physical Therapy (PT). PT will consist of 6 sessions with a licensed physical therapist based on Guide to Physical Therapy Practice 3.0⁵¹ consisting of 1) therapeutic exercise, 2) balance and proprioception, 3) strength training, 4) use of modalities (e.g., heat/cold pack).

Discharge will consist of a second biomechanical motion analysis (**[name]**; Motion and Sports Performance Laboratory at SCH), and exit interview, and self-report questionnaires completed by patient and parent.

Follow-up will occur 3 and 6-months post-discharge assessment. During the follow-up period, patients and parents will be asked to complete 7-days of daily diaries and complete self-report questionnaires.

Table 3. Typical Pain Management Sessions

Session	Topic	Adolescent Content	Parent Content
1	Rapport Building, History	Build rapport; obtain patient history. Discuss goals for treatment.	Joint Session: Same content
2	PT Session 1	Adolescent in Physical Therapy	N/A

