9. STATISTICAL CONSIDERATIONS

9.1 General Design Issues

Aim 1a: *To evaluate pain-related fear outcomes between GET Living and TPM. Hypotheses: Compared to TPM, the GET Living group will (1) have significantly less pain-related fear avoidance (adolescent, parent) at discharge, with continued gains at 3 and 6-month follow-up; Exploratory: (2) have fewer number of days to achieve pain-related fear improvement, assessed via daily diaries.*

Aim 1b: *To evaluate disability and parent responses to pain outcomes between GET Living and TPM. Hypotheses: Compared to TPM, adolescents receiving GET Living will have (1) significantly less functional disability and protective parent responses at discharge, with continued gains at 3 and 6-month follow-up; Exploratory: (2) fewer number of days to achieve decreased functional disability and protective parent responses, assessed via daily diaries; (3) significantly better adolescent joint kinetics at discharge, assessed via motion analysis; and (4) demonstrate significantly greater increases in daily physical activity levels at discharge via actigraphy. We will also examine treatment response correlates: age, pain, gender, diagnosis, and readiness to change.*

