Aim 1 Analysis Plan. GET Living vs. TPM. Linear mixed effects models will be used to compare GET Living to TPM. The outcome of interest for H_{1a} will be FOPQ-C and PFOPOQ total scores. For H_{1b}, outcomes are FDI and ARCS-Protect scores. Exploratory endpoints. Daily Diary (DD): We will use a randomization test (<https://tamalkd.shinyapps.io/scda/>)⁵³ to assess the difference between baseline (BAS) to discharge (END) and BAS to 3 and 6-month follow-up (FU)^{21,54}. We will also examine at what point during treatment significant improvements occur using delayed effect lags (one effect equals 1 day) until p-value 0.05 is reached. Actigraphy: Actilife software will be used to extract data and calculate mean and peak daily activity. Published data reduction methods will be used⁴³. We will model physical activity (mean, peak) at two time points using mixed 2 (time) x 2 (group) ANOVAs. Rate of change in physical activity from BAS to END will also be examined using DD method. Biomechanical assessment: Full body joint kinematic (motion) and kinetic (force) data will be collected with a 20-camera Vicon system (Centennial, CO, USA) with 5 integrated force plates (Bertec; AMTI). Markers will be placed on each participant according to the 3D Plug In Gait model (Vicon) with data recorded and processed in Nexus 2.6.1. Participants will walk, complete the Star excursion balance test and drop jump task^{37,41}. Biomechanical variables (stride length; peak hip and knee extensor moments; peak ankle plantarflexor moment; Star excursion balance score) will be extracted using Event Analyser (Vicon) for error free data reduction. We will model biomechanical variables using mixed 2 (time) x 2 (group) ANOVAs. We will also examine treatment response correlates: age, pain, gender, diagnosis, and readiness to change.

Aim 2: To characterize feasibility of GET Living to inform implementation of a large multi-site RCT.

Hypotheses: GET Living participants will have (1) high treatment satisfaction ratings (mean score ≥ 40 of 60; reflective of satisfied or very satisfied); *Secondary:* (2) $\geq 80\%$ sessions completed on-schedule, $\leq 20\%$ attrition rate, $\geq 80\%$ adolescent and parent daily diary adherence; *Exploratory:* (3) fewer health care costs at 3 and 6-month follow-up compared to TPM.

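### The daily-diary search for the day of improvement steps one day at a time until p reaches 0.05, with no correction for repeated testing, so the reported day does not hold the 5% level

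*Combined protocol and SAP*

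**What the plan says.** Section 9.1 (Aim 1 Analysis Plan) assesses the diaries with a randomization test of baseline against discharge and against the two follow-ups. It then proposes to examine "at what point during treatment significant improvements occur using delayed effect lags (one effect equals 1 day) until p-value 0.05 is reached". Actigraphy is brought under the same approach: "Rate of change in physical activity from BAS to END will also be examined using DD method".

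The hypotheses behind this are between-arm. Section 1.1, hypothesis 1a(2), says that, compared with TPM, the GET Living group will "have fewer number of days to pain-related fear avoidance improvement via daily diaries". Hypothesis 1b(2), restated in Section 9.1, adds "fewer number of days to achieve decreased functional disability and protective parent responses, assessed via daily diaries". Both are labelled exploratory.

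The randomization test rests on a randomized baseline length. Section 3 has the biostatistician create a "randomization scheme to determine the number of days for the pre-treatment baseline period for each individual participant (2 weeks on average"). No range of start days is given.

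The only ceiling on the search is the treatment period, and its length is described inconsistently. For GET Living, Section 3 states "The protocol consists of 12 50-minute sessions delivered twice a week for up to 12 weeks", while Section 5.1 has sessions "delivered twice a week over for up to 6 weeks". For TPM, Section 5.1 has "delivered twice a week, on average for 6 weeks". The Précis gives about 6 weeks of active treatment for every participant.

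**The concern.** Testing at lag 0, 1, 2 and so on, and stopping at the first p of 0.05 or less, gives chance many opportunities. Each test may hold its level, but the search as a whole does not. The plan nevertheless calls the day it finds a significant improvement and cites 0.05. A reader of the results would take a reported improvement day as carrying a 5% error rate.

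The second gap is that the rule produces a day within a series, whereas the hypotheses compare days between arms. Setting two such days side by side is not a test. The day on which p reaches 0.05 also depends on how many diary days there are and how noisy they are, not only on how fast patients improve.

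**Working it through.** **No figure to reproduce.** The document gives no error rate, power or sample size for the diary analysis. Its only adjustment for repeated looks is the O'Brien-Fleming pair in Section 9.4 (0.0054 and 0.0492), which concerns the interim analysis.

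**Inputs from the document.** One-day lag steps and threshold 0.05 (Section 9.1); baseline length randomized, mean 14 days (Section 3); about 6 weeks = 42 treatment days (Précis and Section 5.1); 29 per arm at end of study (Section 9.2).

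**Assumptions, because the text does not settle them.** One-sided test; start day uniform on *k* values centred near day 14; AR(1) diary errors with correlation 0.3 or 0.6; total length T = 14 + 42 = 56 days. The search runs to lag 28, which leaves 56 - 24 - 28 = 4 treatment days for the latest start day, 24.

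**Statistic.** With *s* baseline days and lag *l*:
- Lag days dropped: D = mean(days 1 to s) - mean(days s+l+1 to T).
- Boundary moved: D = mean(days 1 to s+l) - mean(days s+l+1 to T).

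Per participant, p is the share of the *k* possible start days whose D is at least the observed D. Pooled, D is averaged over the arm and compared with 399 re-randomizations of the start days. A false declaration is any p of 0.05 or less at lags 0 to 28 when there is no effect.

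**Smallest attainable p, per participant: 1/k.** 1/15 = 0.067; 1/19 = 0.053; 1/20 = 0.050; 1/21 = 0.048. At least 20 possible start days are needed before any day can be declared.

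**Simulated chance of declaring an improvement day with no effect:**

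| Test level | Start days | Lag 0 only | To lag 28, dropped | To lag 28, moved |
|---|---|---|---|---|
| Per participant | 20 or 21 | 4-5% | 22-24% | 73-79% |
| Arm of 29 | 7 to 21 | 4-6% | 14-20% | 36-60% |
| Per participant | 15 or 19 | 0% | 0% | 0% |

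As a rough guide (not a bound), 29 independent looks would give 1 - 0.95^29 = 77%.

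**Sensitivity.** A separate simulation searched to lag 27 and included uncorrelated errors. For an arm of 37 it gave 10-14% (dropped) and 32-53% (moved). Per participant with 21 start days it gave 15-16% and 71-75%. The percentages shift with the settings, but the direction does not.

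**Correction checked.** Each lag's statistic is standardised over the re-randomizations, and the maximum over all lags searched is referred to its own re-randomization distribution. This brings the pooled rate back to 4-6% in every setting run.

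**Between-arm analysis.** The mixed models in Section 9.1 are tied to the child and parent fear questionnaire totals, the FDI and ARCS-Protect. Section 9.6 says only that mixed models will be used for Aim 1. Neither names days to improvement as an outcome, and neither says how participants who never reach 0.05 are handled.

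**The case against.** The diary outcome is exploratory throughout (Sections 1.1, 9.1 and 9.5.4), and the plan's verb is to examine. No power figure, stopping rule, or primary or secondary test uses it. Multiplicity control in exploratory work is partly a matter of preference. This stands as a limit on importance. It does not rescue the wording, because the plan itself attaches significance and 0.05 to the result.

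The lag sentence names no test, so reading it as the randomization test is an inference, though no other diary test is named. The cited software and papers, which cannot be seen here, may fix the test level, start-day window and lag handling. That also stands: the size of the inflation cannot be pinned to one number, and the larger figures need the moved-boundary reading, which the text does not state.

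Two stronger readings are tempting. A reader might infer that the error rate is close to certainty. Simulation does give about 98% per participant, but only with the boundary moved and the search run to near the end of 84 treatment days. The 12-week length appears only in Section 3, whereas the Précis and Section 5.1 give about 6 weeks. A reader might also infer that the rule favours one arm. The plan states no between-arm comparison of days, so no between-arm bias can be shown from it.

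**Conclusion.** The concern holds as a minor point. Followed as written, the rule yields significant improvement days that do not hold the 0.05 level wherever 0.05 is attainable. Under the settings assumed above, the false-declaration rate over about 6 weeks of treatment is roughly 14-24% with lag days dropped and 36-79% with the boundary moved, against 4-6% for the single test at lag 0. If the test is per participant with fewer than 20 start days, the opposite happens and no day can ever be declared.

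The absence of a between-arm analysis for hypotheses 1a(2) and 1b(2) is confirmed from the text. On its own it is mostly missing detail. It matters here because the lag search is the only stated route to those hypotheses.

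The reach is the diaries, and actigraphy through the cross-reference to the diary method. The primary fear analysis, the secondary disability analysis, the power calculations and the interim rules are untouched.

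**What to change.** In the Aim 1 Analysis Plan of Section 9.1:

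1. Keep the lag-0 randomization test as the only significance test of the phase effect, combined within arm if there are fewer than 20 possible start days.
2. Report lag results as descriptive, with no 0.05 claim, for the diaries and for actigraphy.
3. If a significance claim on timing is wanted, make it at arm level with a max-statistic correction over a stated lag range. Fix that range only after the treatment lengths in Sections 3 and 5.1 have been reconciled.
4. Draw no between-arm conclusion on days to improvement from the lag search unless a between-arm analysis is pre-specified.

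This needs plan wording and, for item 3, modest programming on the same data. The descriptive label costs only the significance claim. The correction costs sensitivity: in pooled simulations of a 0.5-SD drop from treatment day 7, detection was 6-29% instead of 23-52% (lag days dropped), or 24-74% instead of 78-97% (boundary moved). Part of the uncorrected figure is the inflated error rate itself. The descriptive route is therefore the natural default.

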9.2 Sample Size and Randomization

We chose the largest feasible study size to obtain as precise estimates as possible of improvement in adolescent disability while ensuring adequate power for the treatment difference in the improvement in adolescent pain-related fear. This gave us a starting total sample size of 74 (37 in each arm). Based on pilot data, we expect roughly 19% attrition during treatment to a total of 60 and further attrition to 58 at end of follow-up.

Power calculations were first performed using the simplified approach of paired t-tests for the change from baseline to 3 and 6-months on those with 3 and 6-months data. For this approach, we used means and standard deviations of observed changes in pilot data. We then simulated data from our analytic model using the standard deviations at each time point and standard deviations of change to calculate correlation and hence the random effect and error variances. The mixed models simulation allowed us to use more data and yielded slightly higher power estimates.

Primary Outcome: In our primary power calculation, we assumed that the improvement in adolescent pain-related fear at 3 and 6-months would be 22.4 in GET Living and 5 in TPM, a difference of 17.4, with a standard deviation for change of 21. Under this scenario we will have power of 87% with 58 (29 in each arm) at end of study. Under more conservative assumptions, we still have power of 80% with only 52 at the end of study and a treatment difference of 16.6. With a smaller standard deviation of 18.9, we will have power of 80% with 50 at end of study and a treatment difference of 15.4.

Other Outcomes: For parent pain-related fear, our estimated treatment difference at 3 and 6-months is 13 with an estimated standard deviation for change of 8.5. This would give us power close to 100% for 58 at end of study and we would still have 90% power with a treatment difference of only 8 and only 50 left at end of study.

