9.5.4 Exploratory Outcomes

Physical Activity (Actigraphy), Daily Diary (Child and Parent), and Biomechanics (motion analysis) are exploratory outcomes. Actigraphy will be measured during 2-week pre-treatment baseline throughout active treatment. The Daily Diary will be administered for an average of 14 days during the initial baseline period through treatment, and again for 7 days at the 3 and 6-month follow-up time points. Motion analysis will be conducted at Baseline and Discharge sessions.

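### Biomechanics and actigraphy are compared by 2×2 ANOVA, which amounts to a test on change; adjusting for the baseline already collected and for the strata would usually tighten the intervals, by an amount the documents cannot fix

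*Combined protocol and SAP*

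**What the plan says.** The Aim 1 analysis plan in Section 9.1 sets the method by type of outcome. For motion analysis: "We will model biomechanical variables using mixed 2 (time) x 2 (group) ANOVAs". For actigraphy: "We will model physical activity (mean, peak) at two time points using mixed 2 (time) x 2 (group) ANOVAs". For the questionnaires: "Linear mixed effects models will be used to compare GET Living to TPM".

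Baseline values exist for both exploratory families. Section 9.5.4 states "Motion analysis will be conducted at Baseline and Discharge sessions" and "Actigraphy will be measured during 2-week pre-treatment baseline throughout active treatment". The schedule in Section 6.1 agrees. The second actigraphy time point in the ANOVA is not defined; Section 3 says only that monitoring stops at discharge.

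Randomisation is stratified on fear and disability (Sections 3, 6.2.2 and 9.2). No section puts baseline or either stratification factor into the model for these outcomes, and none says how a missing discharge value is handled. Section 9.3 says only that intention-to-treat and per-protocol populations will not be separated.

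Two further statements limit the point. Section 9.1 also plans to study the rate of change in activity with the daily-diary method. Section 9.5.4 sets the status of these measures: "Physical Activity (Actigraphy), Daily Diary (Child and Parent), and Biomechanics (motion analysis) are exploratory outcomes".

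**The concern.** A two-by-two mixed ANOVA takes its treatment effect from the group-by-time term, and that term is the difference between arms in mean change. Subtracting the full baseline value is the best use of it only when baseline and discharge are almost perfectly correlated. Otherwise the subtraction adds baseline noise that a covariate would leave out. The stated model also ignores factors that were used to balance the arms.

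What is at stake is the precision of the arm comparisons for hypotheses (3) and (4) of Aim 1b. The trial is meant to inform a larger multi-site study, and Section 9.2 describes its size as the largest feasible. Precision available from data already collected is therefore worth taking.

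**Working it through.** **Inputs from the documents.** There are 37 per arm at the start, and Section 9.2 says "we expect roughly 19% attrition during treatment to a total of 60 and further attrition to 58 at end of follow-up"; 74 × 0.81 = 59.9, so 30 per arm at discharge. For disability, Section 9.2 gives a difference of 7, an SD of change of 11.2, an SD of 12.6 at each time point, and t-test power of 65% with 58 participants. **Assumed:** equal variances at the two times, a two-sided 5% level, and a range for the correlation r, because none is given for actigraphy or biomechanics.

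**1. Reproduce a stated figure.** The plan gives no power or precision for these two families, so disability is the nearest check. Noncentrality = 7 / (11.2 × √(2/29)) = 2.38. With 56 degrees of freedom, power is 64.8%, against 65% stated. It reproduces.

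**2. The ANOVA is a test on change.** In a generated data set of 60, the group-by-time F was 5.1818 and the squared t on change scores was 5.1818. They are identical.

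**3. Variance.** In units of the single-time variance:
- change score: 2(1 − r)
- adjusted for baseline: 1 − r²
- ratio: (1 + r)/2

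**4. Interval half-widths at 30 per arm, in SD units.**
- Change: √(2(1 − r)) × √(2/30) × 2.0017 (58 df)
- Adjusted: √(1 − r²) × √((2/30)(1 + 1/56)) × 2.0025 (57 df)

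| r | change | adjusted | narrower by |
|---|---|---|---|
| 0.3 | 0.612 | 0.498 | 18.6% |
| 0.5 | 0.517 | 0.452 | 12.6% |
| 0.605 | 0.459 | 0.415 | 9.6% |
| 0.7 | 0.400 | 0.373 | 7.0% |
| 0.8 | 0.327 | 0.313 | 4.3% |
| 0.9 | 0.231 | 0.227 | 1.6% |
| 0.95 | 0.163 | 0.163 | 0.3% |

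The widths are equal at r = 0.96. The value 0.605 is the one implied for disability: 1 − 11.2²/(2 × 12.6²). There the width ratio is 0.904, and (1/0.904)² = 1.22, so 60 participants give the precision of about 73.

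**5. Cost of the strata.** The table counts the baseline term only. Two stratum terms leave 55 df and move the critical value from 2.0025 to 2.0040, under 0.1% of the width if the strata stay balanced across arms. If they explained nothing and were as unbalanced as under simple randomisation, replacing 1 + 1/56 by 1 + 3/54 would cut the gain by just under 2 percentage points (7.0% to 5.2% at r = 0.7, and slightly below zero at 0.9).

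**6. Daily actigraphy with only a participant random intercept.** The arm-by-period term is again a difference in mean changes, so the gains above do not apply to it. Its standard error also leaves out variation between participants in their own change. Assume 14 baseline and 42 treatment days, day-to-day SD 1, and a participant-specific change with SD s. The model takes the variance of one participant's change as about 1/14 + 1/42 = 0.095; the true value is 0.095 + s². For s = 0.2, 0.3 and 0.5, after allowing for the slightly inflated residual, the standard error is too small by factors of 1.19, 1.38 and 1.86. The nominal 5% test then rejects about 10%, 16% and 29% of the time.

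**The case against.** The strongest reply is that the planned test is valid. Under randomisation, and without selective dropout, the change contrast is unbiased, and it matches the wording of Aim 1b(4), which speaks of increases. The outcomes are exploratory and do not drive the sample size. For highly repeatable gait measures r may be 0.9 or more, where the gain is under 2%. All of this stands, and it keeps the point small.

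A reader might also infer more than the documents support:

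- **That the change rescues the roughly 14 of 74 (74 − 60) expected to be lost during treatment.** It does not. Motion analysis has one post-baseline visit, so with baseline as a covariate a participant without a discharge value still contributes nothing. Nor does the plan say that these analyses are restricted to completers. That follows from how a two-time ANOVA normally works, and for actigraphy the undefined second time point leaves room for partial data.
- **That daily actigraphy is reduced to two values and otherwise discarded.** Section 9.1 also plans a rate-of-change analysis by the daily-diary method.
- **That a daily mixed model with a participant random effect is a safe upgrade.** Step 6 shows that it can be anti-conservative.
- **That the questionnaire model already does what is asked here.** Sections 9.1 and 9.6 do not say that it adjusts for baseline or strata.
- **That the gain is unconditional and free.** It depends on r and costs degrees of freedom.

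**Conclusion.** The point holds as a modest gain in efficiency. For both families the planned arm comparison is a change-score test that omits the stratification factors, and no section adjusts for the baseline that is collected. With about 60 participants at discharge, adjusting for baseline narrows the interval by about 19% to 7% for r from 0.3 to 0.7, 4% at 0.8 and 2% at 0.9, with nothing left near 0.96. These figures assume equal variances at the two times, dropout unrelated to baseline, and strata that remain roughly balanced across arms. The true r for stride length, joint moments, balance score and activity is unknown; 0.605 is borrowed from disability and shows scale only.

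Baseline adjustment has a second, smaller merit. If dropout depends on baseline, change scores can be biased. In a deliberately extreme simulation at r = 0.5, with dropout tied to baseline in opposite directions in the two arms, the bias was 0.23 SD for change and about zero after adjustment. Under such dropout the precision gain shrinks, and at r = 0.9 the adjusted interval was slightly wider (0.468 against 0.458).

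The primary conclusion on pain-related fear is not affected.

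**What to change.** In the Aim 1 analysis plan of Section 9.1, replace the two ANOVA sentences with one rule for both families: compare the arms on the discharge value, adjusted for the baseline value, fear stratum and disability stratum (as used at randomisation), and report the adjusted difference with its confidence interval. For actigraphy, define in advance the baseline window and an end-of-treatment window over which daily mean and peak activity are summarised.

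State how participants without a discharge value are handled and report their number by arm, since this change does not bring them back. Keep the planned rate-of-change analysis by the daily-diary method. If a model of daily actigraphy is added, it needs a participant-specific random period effect as well as a random intercept, and an explicit treatment of baseline.

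The cost is wording and about three degrees of freedom (one for baseline, two for the strata). No new data or visits are needed. If r turns out very high, the gain is negligible and the loss is small.
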